--	---

	
 
- Carbon footprint of the intervention or carbon-saving due to the intervention
 

Procedures and measurements	
Objective 1: Improve integrated management of sick children
 
In Phase 1, eligible HFs will be grouped into three implementation blocks of 10-12 health facilities (half intervention and half control). Randomization will not be done for reasons of feasibility and high chance of contamination if control and intervention facilities are mixed and in close proximity to each other as randomized. Therefore, boundaries between groups of intervention and control facilities will be delineated geographically.
 
Sick children will be enrolled throughout Phase 1, as new blocks of facilities are introduced every four months and control facilities are converted into intervention facilities. Children enrolled in intervention facilities will be managed using ePOCT+, with all data associated with the consultation being captured electronically. Children enrolled in control facilities will be assessed, diagnosed and treated as per routine protocols by clinicians. A similar but simplified tablet or PC application will also be used in control facilities to record only outcome measure related data using an electronic case report form.
 
Primary outcome measure: For measuring antibiotics prescribed at initial consultation, the treatment data recorded in the tablets or PCs by HWs throughout the study will be compared between intervention and control facilities, captured electronically in both facility types.
 
Secondary outcome measure: For assessing clinical cure at day 7, a simple questionnaire (asking if the child is still sick, was hospitalized secondarily, or died) will be administered to all caregivers by phone.
 
In Phase 2, all HFs will be using ePOCT+. Indicators monitored over time and space will be measured the same way as in Phase 1, except that clinical cure, secondary hospitalizations and deaths may not be collected or will be assessed through an automated phone call or SMS sent to caregivers using the same simple questionnaire (resource dependent).
 
Secondary analyses will be used to assess differences in the quality of the consultation made by HWs, including the rational use of antimicrobials (antibiotics and antimalarials). Two sources of data will be used and compared between intervention and control facilities:
 
 
- the final decision on referral, tests performed, final diagnoses retained and treatment prescribed will be recorded in the tablets or PCs by HWs at initial consultations and re-attendance visits.
 
- during a cross-sectional quality of care survey, observers in the consultation room will record key symptoms and signs assessed by HWs, diagnostic tests requested, final decision on referral, final diagnoses retained and treatment prescribed.
 
 
Objective 2: Improve the algorithm and adapt it to spatiotemporal variations
 
In Phase 2 of the study, the algorithm will be improved in terms of diagnostic and prognostic accuracy and adapted to local fluctuations in epidemiology, demography, geography and resource availability. Each potential modification will first be evaluated by the Rwandan clinical expert group for its clinical coherence, safety and potential benefit, and then applied to the retrospective data. If these analyses confirm a clinically relevant positive impact, the change in the algorithm will be implemented in all relevant locations/patient sub-groups and monitored based on the indicators relevant to the specific change in the algorithm collected throughout the study through the tablets.
 
Objective 3: Enhance M&E and supportive supervision
 
Patient-level data will also enhance M&E activities and supportive supervision of the HWs through the medAL-monitor/medAL-outbreak platform. Clinicians will use data generated from their own consultations to self-audit their clinical practices by monitoring quality of care indicators in the medAL-monitor dashboards and improve their skills in specific areas using the e-learning platform. Similarly, members of the DHMT will use medAL-monitor to identify and provide support to HFs in need of additional training and mentorship. In time, this enhanced ability to capacitate HWs and

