### 8.1.3 Re-attendance visits in case of persisting or worsening of symptoms

At initial consultation, the advice to caregivers on when to bring the child back to the HF is left at the discretion of the HW. During Phases 1 and 2, HWs will be guided by the ePOCT+ tool, which recommends conditional follow-up based on WHO and national guidelines. At re-attendance visits, whether scheduled or unscheduled, children will be managed in the same way as all other children in that particular facility at that time (ePOCT+ or routine care). If the child comes back to the same HF that uses ePOCT+ as for the initial consultation, the HW will have access to the electronic data of that initial consultation that is saved in the HF tablets. If the child goes to a different HF participating in the study, the HW will not have access to that data. Investigators will however be able to link data collected at different facilities (as long as they are part of the study) for the same child through the unique identification number provided to caregivers. If the child goes to a HF not participating in the study, no data will be available for that consultation. The ePOCT+ registration module, used at all participating facilities, will inquire about the type of visit (initial/scheduled re-attendance/unscheduled re-attendance) and the main reason for that visit.

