2.1.2 Secondary outcomes

All secondary outcomes are compared between the intervention (ePOCT+) and control (routine care) arms.

Percentage of children cured at day 7 in the intervention group (ePOCT+) as compared to the control group (routine care)

Outcome measure: The child is defined as being cured at day 7 if the caregiver says that the child is cured or has improved since the initial consultation. Non-referred secondary hospitalizations (if caregiver says that child was hospitalized between day 0 and day 7 but the electronic clinical data does not indicate a referral for hospitalization) will however be considered as clinical failures even if the child is already cured at day 7.

Timing and method of measurement: Assessment of subjective clinical cure by the caregiver, and history of non-referred hospitalization will be assessed by telephone or home visit follow-up 7 days (range 6-14 days) after enrollment of the subject. The day of enrollment of the subject is considered as day 0.

Analysis type: Superiority

Secondary consultations:

- % of children with one or more unscheduled re-attendance visits at any health facility by day 7

Timing and method of measurement: Telephone or home visit follow-up 7 days (range 6-14 days) after enrollment of the subject. The day of enrollment of the subject is considered as day 0.

Severe outcome by day 7:

- % of children with non-referred secondary hospitalization by day 7
- % of children who have died by day 7

Timing and method of measurement: Death and non-referred secondary hospitalization will be assessed by telephone or home visit follow-up 7 days (range 6-14 days) after enrollment of the subject. The day of enrollment of the subject is considered as day 0.

Primary referrals:

- % of children referred to hospital or inpatient ward at a health centre at initial consultation

Timing and method of measurement: Documented by the HW at the end of the initial consultation in the eCRF (control arm) or in ePOCT+ (intervention arm) when the subject was enrolled (day 0)

Appropriate case management for malaria at initial consultation

- % of febrile children tested for malaria by RDT and/or microscopy at day 0
- % of malaria positive children (positive RDT result OR positive microscopy result) prescribed an antimalarial at day 0
- % of malaria negative children prescribed an antimalarial at day 0
- % of untested children prescribed an antimalarial at day 0

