Timing and method of measurement: Documented by the HW at the end of the initial consultation where the subject was enrolled (day 0)

Definitions:

Clinical cure is a positive answer to the question “Is the child cured?” or if not cured “Has the child improved?” asked to caregiver through a phone call at day 7. Non-referred secondary hospitalizations (see definition below) will be considered as clinical failures even if the child is already cured at day 7.

Clinical failure is a negative answer to the question “Is the child cured?” and “Has the child improved” asked to the caregiver through a phone call at day 7. Non-referred secondary hospitalization (see definition below) will be considered as a clinical failure even if the child is already cured at day 7.

Initial consultation is the first visit of a sick child for an acute problem at a HF participating in the study (and thus registered electronically); timeframe from completion of the initial visit up to midnight of the same day. The initial consultation is considered as day 0.

Re-attendance visit is a consultation (not necessarily at a HF participating in the study) taking place from the day after initial consultation up to day 14 included. A re-attendance visit can be scheduled (proposed by the HW on a certain day) or unscheduled (upon decision by caregivers).

Primary referral is a decision of referring or admitting the child at a hospital or health center for at least one night, taken by the HW at the initial consultation.

Secondary referral is a decision of referring or admitting the child at a hospital or health center taken by the HW during a re-attendance visit taking place from the day after initial consultation up to day 7 included.

Primary hospitalization is an admission to a hospital or health center ward for at least one night taking place the same day as the initial consultation

Secondary hospitalization is an admission to a hospital or health center ward for at least one night taking place from the day after initial consultation up to the phone call at day 7 included. A non-referred secondary hospitalization is a direct visit to hospital without a re-attendance visit the same day at a HF participating in the study. Non-referred secondary hospitalization will be determined if the caregiver reports during the day 7 phone follow-up that the child was hospitalized, even if there was no documentation of a referral from initial and re-attendance visits at participating health facilities.

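### An admission after a recorded referral is neither a severe outcome nor an automatic failure, and no between-arm analysis of all secondary hospitalisations is planned

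*SAP*

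**What the plan says.** SAP 2.1.2 has two severe outcomes by day 7, both compared between arms: the percentage "of children with non-referred secondary hospitalization by day 7" and the percentage "of children who have died by day 7". Non-referred admission also overrides a caregiver's report of cure. For that purpose it is identified "if caregiver says that child was hospitalized between day 0 and day 7 but the electronic clinical data does not indicate a referral for hospitalization".

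The Definitions in the same section use a different test: "A non-referred secondary hospitalization is a direct visit to hospital without a re-attendance visit the same day at a HF participating in the study". Their next sentence can be read as counting every admission the caregiver reports, whether or not a referral was documented.

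The Definitions also include this: "Secondary referral is a decision of referring or admitting the child at a hospital or health center taken by the HW during a re-attendance visit". No listed outcome uses that term. The protocol (7.1) has the same outcome structure.

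The day-7 questionnaire goes to all caregivers, "asking if the child is still sick, was hospitalized secondarily, or died" (Protocol, Synopsis). On return visits, Protocol 8.1.3 says "HWs will be guided by the ePOCT+ tool, which recommends conditional follow-up based on WHO and national guidelines", and Protocol 3.1 says ePOCT+ is used at re-attendance as at the initial visit and guides referral.

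**The concern.** Hypothesis 1 of the protocol is that antibiotic prescribing falls while clinical outcomes stay similar. The harm most directly opposed to that is a child who deteriorates after day 0 and is admitted. The planned severe outcome counts only the admissions labelled non-referred.

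That label is settled after allocation. It depends on whether the child came back to a participating facility, what the health worker decided there and what was recorded. The intervention acts on these steps, and the trial is open-label and non-randomised. A difference between arms in the referred share would move admissions into or out of the counted category without any change in how many children are admitted. What is at stake is the safety conclusion; the primary outcome is untouched.

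**Working it through.** **Step 1: trace one child.** The child is not referred on day 0, returns within the week, is referred (and this is recorded), is admitted the same day, and is followed up at day 6–14.

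| Planned item | Does it register this child? |
|---|---|
| Non-referred secondary hospitalisation | No |
| Death by day 7 | Only if the child dies |
| Clinical failure, symptom route | Only if reported neither cured nor improved |
| Clinical failure, admission override | No |
| Unscheduled re-attendance by day 7 | Yes if the caregiver decided to return; no if the visit was scheduled |
| Primary referral | No, day-0 decisions only |
| Exploratory: hospitalised among those referred (SAP 6.2) | No, referral at the initial consultation only |
| Exploratory: prognostic analysis (SAP 6.2) | Intervention arm only, so not a comparison |

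The child is registered by none of these between-arm outcomes when three things hold together: the return was scheduled, the child survived, and the caregiver reported cure or improvement.

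**Step 2: compare the wordings of non-referred in SAP 2.1.2.**

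| Case | Operational rule (electronic record) | Definitions (same-day visit) |
|---|---|---|
| Referred at re-attendance, admitted that day | Not counted | Not counted |
| Referred at re-attendance, admitted the next day without another visit | Not counted | Counted |
| Sent in by a non-participating facility, no referral in the study record | Counted | Counted |
| Referred on day 0, admitted on day 1 without another visit | Not counted | Counted, read literally |

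The broad reading of the last sentence would count all four. How many admissions are left out therefore depends on which wording is applied.

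**Step 3: how a difference in referred share acts.** The plan's only sample-size figure is for antibiotic prescription, and it reproduces. For 35% versus 26%, two-sided 0.05 and 80% power, n = 410 per arm. The design effect is 1 + (660 − 1) × 0.025 = 17.475, and 410 × 17.475 / 660 = 10.86, rounded up to 11 clusters. It contains no admission rate, so it does not bear on this point.

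Let T be the total secondary hospitalisation rate and f the share that follows a recorded referral (C = control, E = ePOCT+).

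- Counted rate = T × (1 − f)
- Counted ratio = (T_E / T_C) × (1 − f_E) / (1 − f_C)

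T and f are assumed below; only the 10,500 children per arm come from the SAP (3.3).

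| T, C / E | f, C / E | True ratio | Counted events, C / E | Counted ratio |
|---|---|---|---|---|
| 0.5% / 0.5% | 30% / 30% | 1.00 | 36.75 / 36.75 | 1.00 |
| 0.5% / 0.5% | 30% / 60% | 1.00 | 36.75 / 21.0 | 0.57 |
| 0.5% / 0.5% | 60% / 30% | 1.00 | 21.0 / 36.75 | 1.75 |
| 0.5% / 0.75% | 30% / 30% | 1.50 | 36.75 / 55.1 | 1.50 |
| 0.5% / 0.75% | 30% / 60% | 1.50 | 36.75 / 31.5 | 0.86 |
| 0.5% / 0.75% | 60% / 30% | 1.50 | 21.0 / 55.1 | 2.63 |

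Example, row 2: 10,500 × 0.005 × 0.70 = 36.75 and 10,500 × 0.005 × 0.40 = 21.0; 21.0 / 36.75 = 0.57.

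With equal totals the ratio does not depend on T. At 0.25% the 30%/60% case gives 18.4 versus 10.5, and at 1% it gives 73.5 versus 42, again 0.57. A smaller gap of 30% versus 40% gives 0.60 / 0.70 = 0.86. The counted ratio equals the true ratio only when the shares are equal.

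**The case against.** A reader might infer that such a child appears in no between-arm harm analysis, or that non-referred admission is the only severe outcome or route to failure. The documents do not support either. Death is also a severe outcome, a child neither cured nor improved is a failure whether or not referred, and a return on the caregiver's own decision enters the unscheduled re-attendance comparison. The protocol also plans a comparison by arm of referral decisions recorded at initial and re-attendance visits (Synopsis, Procedures and measurements), and sub-analyses of re-attendance visits and of each patient's full visit history (9.2).

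These routes stand, but they are weak substitutes. A child admitted early may have improved under inpatient care by the contact. Unscheduled re-attendance does not separate an admission from a simple repeat visit. Referral decisions are not admissions, and the SAP does not itemise those protocol analyses.

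A reader might also infer that the measure favours ePOCT+. That is not shown. Its follow-up advice rests on WHO and national guidelines, control staff are reminded of IMCI and national guidelines (Protocol 8.1.4), and the SAP (3.1) promises the control arm equivalent clinical training. The gap in referred share could be small or run the other way.

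Finally, counting only non-referred admissions is a consistent choice in both documents. It separates admissions that bypassed the care pathway from referrals that may be appropriate. That is a good reason to keep the measure, but not to leave total admissions uncompared.

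**Conclusion.** The point holds in a limited form. Under the operational rule in SAP 2.1.2, a secondary hospitalisation after a recorded referral is neither a severe outcome nor an automatic failure. No between-arm analysis of all secondary hospitalisations is planned, and indirect capture fails in the scheduled-return case of Step 1.

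The non-referred measure alone can misstate the difference in admissions if referral differs by arm. The direction and size are unknown, because the documents give no admission rate, no referred share and no ICC for this outcome. The ratios of 0.57 and 1.75 show the mechanism under assumed shares and are not forecasts. For the same reason no power can be computed for the added outcome.

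If the broad reading of the Definitions is what the sponsor intends, the gap largely closes, but that reading conflicts with the operational rule and the SAP would have to say so.

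**What to change.** In SAP 2.1.2:

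1. Add as a severe outcome, compared between arms: *percentage of children with any secondary hospitalisation by day 7, referred or not*. Build it from the caregiver's day-7 answer linked to the electronic referral record.
2. Report it with and without children referred or admitted at the initial consultation. Otherwise a child referred on day 0 and admitted on day 1 would be counted as having deteriorated. That error would fall more on the ePOCT+ arm if the tool identifies more children for immediate referral, as Protocol 1.7 expects.
3. Keep the non-referred measure beside it.
4. Add a sensitivity analysis of day-7 cure in which any secondary hospitalisation among children not referred on day 0 counts as failure.
5. Reconcile the conflicting wordings of non-referred in the same edit, and apply the agreed one to both the severe outcome and the cure override.

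The cost is SAP wording and one or two more models. The hospitalisation question is already asked. Separating same-day from later admissions also needs an admission date or equivalent; the documents at hand do not show whether the questionnaire records one, so this should be checked. A small downside is that the total includes some appropriate referrals, which is why the non-referred measure stays.

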**Definitions used for the outcome measures and indicators of objective 1**

- Clinical cure is a positive answer to the question “Is the child cured?” OR “Has the child improved?” (if not cured) asked to caregiver through a phone call or SMS (or home visit) at day 7. Non-referred secondary hospitalizations (see definition below) will however be considered as clinical failures even if the child is already cured at day 7.
- Initial consultation is the first visit of a sick child for an acute problem at a HF participating in the study (and thus registered electronically); timeframe from completion of the initial visit up to midnight of the same day.
- Re-attendance visit is a consultation (not necessarily at a HF participating in the study) taking place from the day after initial consultation up to day 7 included. A re-attendance visit can be scheduled (proposed by the HW on a certain day) or unscheduled (upon decision by caregivers).
- Primary referral is a decision of referring the child to hospital taken by the HW at the initial consultation.
- Secondary referral is a decision of referring the child to hospital taken by the HW during a re-attendance visit taking place from the day after initial consultation up to day 7 included.
- Primary hospitalization is an admission to a hospital ward taking place the same day as the initial consultation
- Secondary hospitalization is an admission to a hospital ward taking place from the day after initial consultation up to the phone call at day 7 included. A non-referred secondary hospitalization is a direct visit and admission to a hospital without a re-attendance visit the same day at a HF participating in the study.
- Antibiotic prescription is any oral, intramuscular or intravenous (but not topical) antibiotic prescribed by a HW during the initial consultation or a re-attendance visit.
- Antimalarial prescription is any oral, rectal, intramuscular or intravenous antimalarial prescribed by a HW during the initial consultation or a re-attendance visit.

- Febrile child is a child with a history of fever and/or a high temperature
- Malaria testing is a malaria RDT or microscopy ordered by a HW during an outpatient visit
- Day 7 is a range of 6-14 days post initial consultation to allow for completion of home visit for children whose caregiver reports having no phone / no phone number.

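### Events labelled 'by day 7' have conflicting end-points: hospitalization is counted up to a contact on any of days 6-14, and re-attendance runs to day 7 or to day 14

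*SAP*

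**What the plan says.** SAP 2.1.2 defines three event outcomes with a day-7 limit in the title: unscheduled re-attendance, non-referred secondary hospitalization and death (the last as the percentage "of children who have died by day 7"). All three are ascertained at one follow-up contact. For the two severe outcomes the text is: "Death and non-referred secondary hospitalization will be assessed by telephone or home visit follow-up 7 days (range 6-14 days) after enrollment".

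The definitions in the same section use other end-points:

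- **Hospitalization.** A secondary hospitalization is an admission "taking place from the day after initial consultation up to the phone call at day 7 included"; Protocol 7.1 ends it at the same call. The SAP adds that a non-referred one is "determined if the caregiver reports during the day 7 phone follow-up that the child was hospitalized", with no limit on the admission date.
- **Day 7 itself.** Protocol 7.1 says: "Day 7 is a range of 6-14 days post initial consultation to allow for completion of home visit". Protocol 8.1.6 gives weekends and repeated call attempts as further reasons for the range.
- **Re-attendance.** The SAP counts visits "from the day after initial consultation up to day 14 included"; Protocol 7.1 counts those "taking place from the day after initial consultation up to day 7 included".

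Other text points to a fixed 7-day period. The footnote to the outcomes in the protocol synopsis limits the hospitalizations that count as failures to those within 7 days. The cure outcome in SAP 2.1.2 refers to hospitalization from day 0 to day 7. Protocol 9.2 considers re-attendance visits over the same days.

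**The concern.** Two analysts following these documents could code the same child differently, because no rule says which end-point governs. If the SAP definition of hospitalization is followed as written, the counting period depends on when the family was reached.

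These outcomes carry the second half of Hypothesis 1 (Protocol 2.1), that antibiotic prescribing falls while clinical outcomes stay similar. SAP 6.1 expects only about 3% not cured at day 7, so small artefacts are not automatically negligible. Late contact also acts in two directions: it gives more time for an admission, re-attendance or death to be counted, and more time for the child to recover before being scored as cured.

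**Working it through.** **Plan's own figures.** The documents give no power or precision figure for these outcomes; the only stated quantity is the 6-14 day contact range. The SAP's minimum of 11 clusters per arm reproduces from its inputs (35% against 26%, two-sided 0.05, 80% power, ICC 0.025, cluster size 660): 410 per arm x (1 + 659 x 0.025 = 17.475) / 660 = 10.86. It rests on the day-0 primary outcome and is not affected.

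**Coding three children under the texts as written**

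- Admitted directly to hospital on day 10, home visit on day 12: a non-referred secondary hospitalization, and so a clinical failure, under the SAP definitions. Not counted under the SAP cure outcome or the synopsis footnote.
- First unscheduled visit on day 10, contact on day 12: a re-attendance under the SAP definition, but not under Protocol 7.1 or the outcome's own title.
- Contacted on day 6, admitted on day 7: the event falls within the label but cannot be reported.

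**Observation time between children.** Counting from the day after the initial consultation to the contact, the extremes are 14 and 6 days: 14/6 = 2.33. Against a day-7 contact the maximum is 14/7 = 2.0. A phone owner reached on the fourth extra attempt, assuming daily calls from day 7, is contacted on day 11: 11/6 = 1.83.

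**Illustration between arms.** The only phone figures are household ownership of 56% in Nyamasheke and 69% in Rusizi (Protocol Table 5, from the 2014-2015 survey). Assume, as an extreme, that one arm has each figure, that all calls fall on day 7, and that every family without a phone is visited on day v. Mean days observed:

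- v = 10: (0.56 x 7 + 0.44 x 10) / (0.69 x 7 + 0.31 x 10) = 8.32 / 7.93 = 1.049
- v = 12: 9.20 / 8.55 = 1.076
- v = 14: 10.08 / 9.17 = 1.099

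Under a constant hazard and rare events these are the spurious event ratios. If every call fell on day 6 and every visit on day 14, the ratio would be 9.52 / 8.48 = 1.12.

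A constant hazard is hard to defend in acute illness. Let the cumulative share of events by day t be 1 - 2^(-t/h), with h the half-life of event timing. With calls on day 7 and visits on day 14:

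- h = 7 days: (0.56 x 0.50 + 0.44 x 0.75) / (0.69 x 0.50 + 0.31 x 0.75) = 0.610 / 0.5775 = 1.06
- h = 3 days: 1.02
- h = 1.5 days: 1.005

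**Cure status.** Take the SAP's 3% failure at day 7 and assume 1.5% at day 12 (no document gives this). The same split gives 0.69 x 3 + 0.31 x 1.5 = 2.54% against 0.56 x 3 + 0.44 x 1.5 = 2.34%, a difference of 0.2 points. With 10,500 per arm the standard error of such a difference is about 0.21 points, before clustering or loss to follow-up.

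**Effect of a fixed cut-off.** Counting dated events only through day 7 lowers the maximum ratio from 2.33 to 7/6 = 1.17 if day-6 contacts remain, and to 1.00 if contact starts on day 7.

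**The case against.** The best defence is that the plan already intends a 7-day period. The outcome titles say so, as do the synopsis footnote, the cure outcome and Protocol 9.2, and the 6-14 day range can be read as a contact window only. The day-14 limit on re-attendance matches the 14-day illness-episode rule in Protocol 6.1 and 9.2 and may have been carried over from it. This is a fair account of the likely intention. It does not settle the matter: the hospitalization definition ends at the contact in both documents, Protocol 7.1 defines day 7 as a range, and no text says which governs. For death, counting to the contact is an inference from that definition and from the absence of a cut-off.

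A reader might infer that follow-up length tracks phone ownership and so differs by arm. The documents do not show this. Protocol 8.1.6 gives weekends and repeat calls as reasons for late contact too, so phone owners can be reached late, and neither document says on which day home visits occur. SAP 3.2 places facilities in three geographic blocks and then splits each block into arms, which is not a contrast of one district with the other. SAP 5.4 tabulates facilities by district and arm, and SAP 6.1 adjusts for imbalanced baseline characteristics. These protections are partial: phone access and contact mode are not among the listed characteristics, and the model has no term for contact day.

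The follow-up questionnaire (Appendix A2) is listed but not reproduced, so event dates may already be recorded.

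**Conclusion.** The conflict in end-points is established from the text and needs no assumption. Following the SAP definitions as written, events on days 8-14 can be counted for children contacted late, and day-7 events are missed after a day-6 contact.

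The 2.3-fold figure is the maximum ratio of observation time between two children. It should not be read as a ratio of risk or as a difference between arms. Bias in the comparison requires contact timing to differ by arm, which geographic allocation makes possible and the documents do not demonstrate. Under the extreme split, with calls on day 7, the spurious event ratio is about 1.10 with a constant hazard and all visits on day 14, and 1.06 to 1.005 if events cluster early. If the arms are similar in contact timing, the bias is small. The cure illustration, resting on an assumed 1.5%, is under one standard error, and it ignores that late-counted admissions are scored as failures, which partly offsets extra recovery.

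The primary outcome is untouched. The point merits correction because it is a real ambiguity in the safety outcomes and is cheap to remove.

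**What to change.** 1. Open the contact window on day 7 (7-14) in both documents.
2. Record the contact date and the date of each hospitalization, re-attendance and death, if these are not already captured.
3. For every by-day-7 outcome, including the hospitalization component of cure, count only events dated day 1 to day 7. Replace the wording that ends hospitalization at the contact ("up to the phone call at day 7 included").
4. Use day 7 as the re-attendance window for this outcome in both documents, and keep 14 days only as the illness-episode rule.
5. Cure status cannot be back-dated. Report contact day and contact mode by arm, and adjust for contact day in a sensitivity analysis. Do not rely on restricting to early contacts such as days 7-9, since that selects against families without phones.

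The cost is wording in two documents and, at most, a few date fields in a questionnaire already administered. Slightly fewer events will be counted, caregivers will misremember some dates, and the option of calling a day early is lost.
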